6.1.3.4. Hypertension

Management of orteronel dosing for different stages of hypertension is outlined in Table 7.

Worsening or new onset hypertension may be part of the natural history of the patients' hypertensive disease, but may also be related to increased adrenal mineralocorticoid activity as a result of increased ACTH secretion induced by relatively nonspecific inhibition of 17-hydroxylase. Reduced potassium or increased serum sodium may be additional indicators of increased mineralocorticoid effect.

If new onset or worsening of established hypertension occurs and the potassium level is <3.5 mEq/L in the absence of other causes such as new diuretic therapy, it suggests a orteronel-related mineralocorticoid syndrome. A plasma renin activity that is undetectable or low also suggests such a syndrome rather than a secondary cause. While addressing either underlying factors or compliance with current antihypertensives, dosing of orteronel should be followed as outlined in Table 7.

CONFIDENTIAL

STUDY DRUG: Orteronel

SCRI INNOVATIONS STUDY NUMBER: BRE 203

DATE OF PROTOCOL: Version 3.0 30 October 2013

Table 7**Criteria and Appropriate Actions for Hypertension**

CTCAE Grade	Event Definition	Action Required
1	Pre-hypertension (systolic BP 120 to 139 mmHg or diastolic BP 80 to 89 mmHg)	No dose modification needed; increase the frequency of BP monitoring as necessary
2	Stage 1 hypertension (systolic BP 140 to 159 mmHg or diastolic BP 90 to 99 mmHg); medical intervention indicated; recurrent or persistent (≥ 24 hrs); symptomatic increase by >20 mmHg (diastolic) or to $>140/90$ mmHg if previously within normal limits (WNL); monotherapy indicated.	Concomitant anti-hypertensive agents may initially be administered without dose reduction. If Grade 2 hypertension persists, dose reduction should follow guidelines in Section 6.1.1.2. Supportive care regimen should follow local standard of care
3	Stage 2 hypertension (systolic BP ≥ 160 mmHg or diastolic BP ≥ 100 mmHg); medical intervention indicated; more than 1 drug or more intensive therapy than previously used indicated	Interrupt orteronel treatment and follow the guidelines in Section 6.1.1.1. Supportive care regimen should follow local standard of care
4	Life-threatening consequences (eg, malignant hypertension, transient or permanent neurologic deficit, hypertensive crisis); urgent intervention indicated	Discontinue orteronel Supportive care regimen should follow local standard of care

Source: CTCAE Version 4.0

Abbreviations: BP = blood pressure; WNL = within normal limits

6.1.3.5. Possible or Suspected Adrenal Insufficiency

If patients experience adrenal insufficiency, the adrenal insufficiency will have the more nonspecific manifestations of glucocorticoid insufficiency, rather than the more specific electrolyte abnormalities of mineralocorticoid insufficiency. Patients experiencing severe physiological stress (eg, surgery, severe infection) should be carefully monitored for adrenal insufficiency. Concomitant medications may complicate the picture of adrenal insufficiency, in particular in patients who are on beta-blockers or diuretics. Concomitant illness such as infection might similarly trigger or worsen symptoms of otherwise mild adrenal insufficiency.

Grading of adrenal insufficiency, the clinical manifestations associated with the specific grade, and management and dosing modifications of orteronel are provided in Table 8. In all cases, actions should include a thorough review for other possible causes or contributors to the presenting symptoms (eg, infection, anemia, or newly introduced concomitant medications).

CONFIDENTIAL

STUDY DRUG: Orteronel

SCRI INNOVATIONS STUDY NUMBER: BRE 203

DATE OF PROTOCOL: Version 3.0 30 October 2013

Table 8 Criteria and Appropriate Actions for Adrenal Insufficiency

Severity	Symptoms/Signs	Action Required/Study Drug Modifications
Possible mild insufficiency	Chronic Grade 1 or Grade 2 fatigue, anorexia <5% weight loss BP normal, possible mild orthostatic hypotension Weight loss	Review medications, check electrolytes, cortisol, and ACTH concentrations Continue study drug as per protocol
Possible or probable moderate adrenal insufficiency, acute or chronic	Grade 2 or 3 fatigue, anorexia, intermittent nausea and vomiting, orthostatic lightheadedness, or weakness Weight loss Definite orthostatic hypotension or below baseline supine BP Possible hyponatremia	Interrupt dosing of orteronel Review medications, check electrolytes, cortisol, and ACTH concentrations Review medications and new diuretic use Dose reduction follows Grade 3 guidelines in Section 6.1.1.1. Discuss with Medical Monitor before restarting orteronel
Possible or probable severe chronic or acute adrenal insufficiency	Grade 3 fatigue, definite anorexia, nausea and vomiting Severe orthostatic symptoms Prostration Nausea and/or vomiting Hypotension at rest and unable to stand due to orthostatic hypotension, possible hyponatremia	Interrupt dosing of orteronel Manage in an acute care facility Administer IV hydrocortisone and electrolyte/volume replacement Review medications, check electrolytes, cortisol, and ACTH concentrations Dose reduction follows Grade 3 guidelines (Section 6.1.1.1) if a reversible precipitating cause can be identified and reversed. Discuss with Medical Monitor before restarting orteronel Discontinue orteronel permanently if a reversible precipitating cause cannot be identified and reversed or in the event of Grade 4 toxicity

Sources: Arlt and Allolio, 2003, Fauci, 2008, and Salvatori, 2005

Abbreviations: ACTH = adrenocorticotrophic hormone; BP = blood pressure; IV = intravenous.

6.1.3.6. Rash (Acneiform or Maculopapular, Localized or Generalized)

Acneiform rash is defined as a disorder characterized by an eruption of papules and pustules, typically appearing in face, scalp, upper chest, and back. Maculopapular rash is defined as a disorder characterized by the presence of macules (flat) and papules (elevated). Also known as morbilliform rash, it is one of the most common cutaneous AEs.

Other types of dermatitis may occur during study treatment; some may require dose modification and supportive care.

Orteronel should be immediately discontinued in a patient experiencing Grade 3 or 4 Stevens-Johnson Syndrome.

CONFIDENTIAL

STUDY DRUG: Orteronel

SCRI INNOVATIONS STUDY NUMBER: BRE 203

DATE OF PROTOCOL: Version 3.0 30 October 2013

Table 9 presents the CTCAE Criteria (Version 4.0) for rash and the appropriate actions to be followed.

Table 9 CTCAE Criteria and Appropriate Actions for Rash (Acneiform or Maculo-papular, Localized or Generalized)

CTCAE Grade	AE	Event Definition	Action Required
1	Acneiform Rash	Papules and/or pustules covering < 10% BSA, which may or may not be associated with symptoms of pruritus or tenderness	No dose reduction is necessary. Topical steroids and/or antibiotics as necessary. Reassess after 2 weeks.
	Maculo-papular Rash	Macules/papules covering < 10% body surface area (BSA) with or without symptoms (eg, pruritus, burning, tightness)	No dose reduction is necessary. Topical steroids and/or antibiotics as necessary. Reassess after 2 weeks.
2	Acneiform Rash	Papules and/or pustules covering 10% to 30% BSA, which may or may not be associated with symptoms of pruritus or tenderness; associated with psychosocial impact; limiting instrumental ADL	Follow guidelines for intolerable Grade 2 toxicity (Section 6.1.1.2). Topical steroids and/or antibiotics as necessary. Other types of systemic treatment such as antihistamine may be required. Repeat incidence of Grade 2 skin rash may require prophylactic antihistamine treatment.
	Maculo-papular Rash	Macules/papules covering 10% to 30% BSA with or without symptoms (eg, pruritus, burning, tightness); limiting instrumental ADL	Follow guidelines for intolerable Grade 2 toxicity (Section 6.1.1.2). Topical steroids and/or antibiotics as necessary. Other types of systemic treatment such as antihistamine may be required. Repeat incidence of Grade 2 skin rash may require prophylactic antihistamine treatment.

CONFIDENTIAL

STUDY DRUG: Orteronel

SCRI INNOVATIONS STUDY NUMBER: BRE 203

DATE OF PROTOCOL: Version 3.0 30 October 2013

CTCAE Grade	AE	Event Definition	Action Required
3	Acneiform Rash	Papules and/or pustules covering >30% BSA, which may or may not be associated with symptoms of pruritus or tenderness; limiting self care ADL; associated with local super-infection with oral antibiotics indicated	Follow guidelines for Grade 3 toxicities in Section 6.1.1.1. Systemic treatment may be considered, including the use of short-term oral steroid (eg, prednisone up to 20 mg), tapering over 7 to 10 days. Monitor signs of GI AEs when prednisone dose is increased. Before adding another oral steroid, consider other options including a combination of topical and oral treatment.
3	Maculo-papular Rash	Macules/papules covering >30% BSA with or without associated symptoms; limiting self care ADL	Follow guidelines for Grade 3 toxicities in Section 6.1.1.1. Systemic treatment may be considered, including the use of short-term oral steroid (eg, prednisone up to 20 mg), tapering over 7 to 10 days. Monitor signs of GI toxicity when prednisone dose is increased. Before adding an oral steroid, consider other options including a combination of topical and oral treatment.
4	Acneiform Rash	Papules and/or pustules covering any % BSA, which may or may not be associated with symptoms of pruritus or tenderness and are associated with extensive super-infection with IV antibiotics indicated life-threatening consequences	Discontinue orteronel.
	Maculo-papular Rash	Not applicable	

Source: CTCAE Version 4.0

Abbreviations: ADL = activities of daily living; BSA = body surface area; GI = gastrointestinal;
IV = intravenous

6.1.3.7. Renal Disorders

The toxicity grade of acute renal injury will be assessed based on the serum creatinine level. Other clinical signs and symptoms, including proteinuria and hematuria, as detected by qualitative or quantitative laboratory tests, may be monitored in addition to creatinine value.

CONFIDENTIAL

STUDY DRUG: Orteronel

SCRI INNOVATIONS STUDY NUMBER: BRE 203

DATE OF PROTOCOL: Version 3.0 30 October 2013

Table 10 presents the appropriate actions to be followed in the event of increased creatinine.

Table 10 **Orteronel Treatment Modification for Acute Renal Disorder**

CTCAE Grade	Event Definition	Action Required
1	Creatinine level increase of ≥ 0.3 mg/dL; creatinine 1.5 to 2 times above baseline	Evaluate patient for urinary tract infection, volume depletion or sub (acute) obstruction. If creatinine remains ≤ 2 times above baseline, no dose adjustment is required.
2	Creatinine >2 to 3 times above baseline	Evaluate patient for urinary tract infection, volume depletion or sub(acute) obstruction. Hold study drug for 2 weeks. Resume at reduced dose level (200 mg BID) once creatinine is ≤ 2 times baseline. If the event recurs, discontinue orteronel.
3	Creatinine >3 times baseline or >4.0 mg/dL; hospitalization indicated	Hold study drug until the patient is discharged from the hospital and creatinine level has recovered to <2 times baseline. Follow guidelines for Grade 3 toxicities in Section 6.1.1.1.
4	Life-threatening consequences; dialysis indicated	Discontinue orteronel permanently.

Source: CTCAE Version 4.0

6.1.3.8. Abnormal Liver Function Tests

The incidence of liver function abnormalities is expected to be low. Grade 2 or 3 abnormal liver function tests (LFTs) that are considered by the investigator to be possibly related to orteronel administration should be managed as appropriate, using Table 11 as a guide. A decision to re-challenge and/or resume dosing at a lower dose should be reviewed with the Monitor in all cases.

CONFIDENTIAL

STUDY DRUG: Orteronel

SCRI INNOVATIONS STUDY NUMBER: BRE 203

DATE OF PROTOCOL: Version 3.0 30 October 2013

Table 11 Management of Abnormal AST and ALT Bearing a \geq Possible Relationship to Orteronel Treatment

AST and/or ALT Elevation Grade (per NCI CTCAE)	Concurrent Bilirubin Level	Required Orteronel Dose Modification
Grade 1	$\geq 1.5 \times$ ULN	Hold until bilirubin resolves to $<1.5 \times$ ULN Reduce dose to 200 mg BID, if receiving 300 mg BID, otherwise discontinue orteronel
Grade 2	$<1.5 \times$ ULN	Hold until ALT/AST resolve to Grade 1 Reduce dose to 200 mg BID, if receiving 300 mg BID, otherwise discontinue orteronel
Grade 2	$\geq 1.5 \times$ ULN	Discontinue orteronel
Grade 3/4	Any	Discontinue orteronel

Note: Following orteronel dose de-escalation due to AST/ALT and/or bilirubin abnormalities, no re-escalation is permitted.

Abbreviations: ALT = alanine aminotransferase; AST = aspartate aminotransferase; BID = twice daily; NCI CTCAE = National Cancer Institute Common Terminology Criteria for Adverse Events; ULN = upper limit of normal

7. STUDY ASSESSMENTS AND TREATMENT

7.1. Overview

All patients should visit the study center on the days specified within this protocol. The complete schedule of assessments is presented in Appendix E.

7.2. Pre-Screening

Patients must sign a pre-screening ICF and provide an archived tumor sample from a primary biopsy or metastatic lesion for centralized testing of AR expression. Those with AR expression $\geq 10\%$ are eligible for entry into the main study. Patients may enroll based on local laboratory AR assessment, but will need to submit tissue for confirmation at the central laboratory.

7.3. Full Screening

Consent for the main study must be obtained ≤ 28 days prior to the initiation of study treatment. The baseline assessments described in Appendix E will be collected prior to the initiation of treatment. Baseline ECHO/MUGA should be within 28 days of treatment.

The physical examination, ECOG performance status, serum/urine pregnancy test (for women of child-bearing potential only), and complete blood counts (CBCs) should be done ≤ 7 days prior to initiation of treatment. All other assessments should be performed ≤ 4 weeks prior to initiation of treatment.

- Signed informed consent prior to any other study-related procedures
- Medical history (including assessment of baseline signs and symptoms)

CONFIDENTIAL

STUDY DRUG: Orteronel

SCRI INNOVATIONS STUDY NUMBER: BRE 203

DATE OF PROTOCOL: Version 3.0 30 October 2013

- Physical examination including measurements of height, weight, and vital signs (resting heart rate, blood pressure, respiratory rate, and oral temperature)
- Eastern Cooperative Oncology Group Performance Status (ECOG) performance status (Appendix A)
- Concomitant medication review at the time of informed consent
- Complete blood count (CBC) including 3-part differential and platelets) (may be done up to 72 hours prior to treatment)
- Comprehensive metabolic profile (CMP) (Section 7.6.3) (may be done up to 72 hours prior to treatment)
- Fasting plasma glucose, insulin, c-peptide, and HbA_{1c} (only in patients with a history of diabetes)
- Serum amylase, lipase
- Serum hormone levels: estradiol, total and free testosterone, SHBG, ACTH, DHEA-S, and cortisol
- Serum/urine pregnancy test (for women of childbearing potential only). If done within 72 hours prior to treatment, this test need not be repeated on Cycle 1 Day 1.
- 12-lead ECG
- ECHO/MUGA
- Urinalysis
- CT scan of the chest/abdomen/pelvis
- Bone scan, if clinically indicated
- CT/MRI of the brain, if clinically indicated

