3.2. Exclusion Criteria

Patients who meet any of the following criteria will be excluded from study entry:

1. Known hypersensitivity to orteronel or to orteronel excipients, which are listed by formulation in the IB
2. Patients receiving other treatment for breast cancer (includes standard hormonal therapy, chemotherapy, biologic therapy, immunotherapy, or radiation therapy). Patients receiving chronic bisphosphonate or denosumab therapy are eligible.
3. Female patients who are both lactating and breastfeeding or have a positive serum/urine pregnancy test during the screening period.
4. Prior anti-androgen therapy
5. Use of an investigational drug \leq 21 days or 5 half-lives (whichever is shorter) prior to the first dose of orteronel, or concurrent treatment. For investigational drugs for which 5 half-lives is less than 21 days, a minimum of 10 days between termination of the investigational drug and administration of orteronel is required.
6. Active brain metastases or leptomeningeal disease. Previously treated brain metastases are allowed provided lesions are stable for at least 3 months as documented by head CT scan or magnetic resonance imaging (MRI) of the brain. Patients must be off steroids, but anti-convulsants are allowed.
7. Patients with known adrenal insufficiency, or patients receiving treatment with ketoconazole, abiraterone, or aminoglutethimide.
8. Wide field radiotherapy (including therapeutic radioisotopes such as strontium 89) administered \leq 28 days or limited field radiation for palliation \leq 7 days prior to starting study drug or has not recovered from side effects of such therapy.
9. Major surgical procedures \leq 28 days of beginning study treatment or minor surgical procedures \leq 7 days. No waiting is required following port-a-cath placement.
10. Presence of active gastrointestinal (GI) disease or other condition that will interfere significantly with the absorption, distribution, metabolism, or excretion of oral therapy (eg, ulcerative disease, uncontrolled nausea, vomiting, diarrhea \geq Grade 2, and malabsorption syndrome).

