5.2.1. Blood samples for measuring serum hormone levels

Blood samples will be collected at baseline, on Cycle 2 Day 1, on Cycle 4 Day 1, and at the End-of-Treatment Visit to test for serum levels of estradiol, total and free testosterone, SHBG, ACTH, DHEA-S, and cortisol. A blood sample will be collected for this purpose from each patient at the noted time points (see Appendix E) and submitted to a laboratory for testing. Details of the laboratory will be provided to the site by the study team. When the results are received by the site, they will be entered into the appropriate eCRF page.

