7.4.1. Day 1 of Each Cycle

The following assessments will be performed on Day 1 of each cycle:

- Medical history
- Physical examination including measurements of weight and vital signs (resting heart rate, blood pressure, respiratory rate, and oral temperature) (**weekly during Cycle 1 for Lead-in patients**)
- ECOG performance status
- AE assessment (**weekly during Cycle 1 for Lead-in patients**)
- Concomitant medication review (**weekly during Cycle 1 for Lead-in patients**)
- CBC, including 3-part differential and platelets (Day 1 of each cycle ± 3 days) (**weekly during Cycle 1 for Lead-in patients**)(need not be done on Cycle 1 Day 1 if baseline was taken within 72 hours of that day)

CONFIDENTIAL

STUDY DRUG: Orteronel

SCRI INNOVATIONS STUDY NUMBER: BRE 203

DATE OF PROTOCOL: Version 3.0 30 October 2013

- CMP (Day 1 of each cycle \pm 3 days) (**weekly during Cycle 1 for Lead-in patients**) (need not be done on Cycle 1 Day 1 if baseline was taken within 72 hours of that day)
- Serum hormone levels: estradiol, total and free testosterone, SHBG, ACTH, DHEA-S, and cortisol (**Day 1 of Cycles 2, 4 and End of Treatment only** [see Section 7.5])
- Serum amylase/lipase
- Serum/urine pregnancy test (for women of childbearing potential only). If the baseline reading was done within 72 hours of Cycle 1 Day 1, this test need not be repeated on that day.
- Study drug compliance assessment

7.4.2. Day 1 of Cycle 3 and Every Other Cycle Following (Cycles 5, 7, 9, etc), except where noted

- Fasting plasma glucose, insulin, c-peptide, and HbA_{1c} (only in patients with a history of diabetes)
- 12-lead ECG
- CT scan of the chest /abdomen/pelvis (only those scans abnormal at baseline need to be repeated)
- Bone scan (if clinically indicated)
- CT/MRI of the brain (if clinically indicated)

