Appendix E: Schedule of Assessments for BRE 203 (continued)

- ^a Physical examinations will include measurements of vital signs (resting heart rate, blood pressure, respiratory rate, oral temperature). At the baseline visit only, height will also be recorded and weight will be recorded only on Day 1 of each cycle.
- ^b Hematological parameters include the following laboratory tests: complete blood count consisting of red blood cell count (RBCs), hemoglobin, total white blood count (WBC) with differential, and platelet count. Do not repeat on C1D1, if baseline within 72 hours.
- ^c CMP assessment includes the following laboratory tests: glucose, BUN, creatinine, sodium, potassium, chloride, calcium, CO₂, alkaline phosphatase (ALP), AST, ALT, total bilirubin, total protein, and albumin. Do not repeat on C1D1, if baseline within 72 hours.
- ^d Fasting plasma glucose, insulin, and c-peptide will be drawn at screening, predose on Day 1 of odd-numbered cycles (Cycles 3, 5, 7, etc), and at study completion for patients with a history of diabetes.
- ^e A single ECG will be obtained at baseline for QTcF interval assessment for all patients. A single ECG will also be obtained predose on Cycle 3 Day 1 and then every 2nd cycle (Cycles 5, 7, 9, etc).
- ^f Archived tumor tissue from a primary biopsy or metastatic lesion is required for centralized testing of AR expression. Patients with AR expression $\geq 10\%$ will be screened for enrollment into the study. Additional tumor tissue, if available from the patients enrolled on study, will be retained to perform correlative testing (15 to 20, 4 um unstained slides). Patients may enroll based on local laboratory AR assessment, but will need to submit tissue for confirmation at the central laboratory.
- ^g Informed consent must be obtained ≤ 28 days prior to the initiation of trial treatment. The physical examination, ECOG performance status, serum/urine pregnancy test (for women of child-bearing potential only), and complete blood counts (CBCs) should be done ≤ 7 days prior to initiation of treatment.
- ^h If clinically indicated.
- ⁱ Day 1 of each cycle following Cycle 1
- ^j Serum hormone levels will be drawn at screening, on Day 1 of Cycles 2 and 4, and at the end of study visit.
- ^k Do not repeat on Cycle 1 Day 1, if baseline was done within 72 hours.
- ^l Lead-in patients only
- ^m If no documented progressive disease and the last assessment was >8 weeks prior. Only abnormal scans at baseline need to be repeated.

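### The only baseline hormone sample may be drawn up to 4 weeks before dosing, with no link to the end of prior endocrine therapy or steroids and no set time of day, so the descriptive hormone changes can be biased

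*Combined protocol and SAP*

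**What the plan says.** **Timing of the sample.** Section 7.3 sets two windows. The physical examination, ECOG status, pregnancy test "and complete blood counts (CBCs) should be done ≤ 7 days prior to initiation of treatment". For everything else, "All other assessments should be performed ≤ 4 weeks prior to initiation of treatment". The panel is listed there as "Serum hormone levels: estradiol, total and free testosterone, SHBG, ACTH, DHEA-S, and cortisol" with no tighter timing, whereas the CBC and metabolic profile carry a 72-hour note. Section 5.2.1 says "Blood samples will be collected at baseline, on Cycle 2 Day 1, on Cycle 4 Day 1, and at the End-of-Treatment Visit". Section 7.4.1 limits the later draws to "Day 1 of Cycles 2, 4 and End of Treatment only", and Appendix E footnote j confirms the scheme: "Serum hormone levels will be drawn at screening, on Day 1 of Cycles 2 and 4, and at the end of study visit". No section gives a clock time or a relation to the dose for these samples.

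**Prior therapy.** Exclusion 2 in Section 3.2 bars "Patients receiving other treatment for breast cancer (includes standard hormonal therapy, chemotherapy, biologic therapy, immunotherapy, or radiation therapy" but gives no interval since the last such treatment. Exclusions 5, 8 and 9 do give intervals, for investigational drugs, radiotherapy and surgery. The interval in exclusion 5 runs to the first dose, not to the baseline sample: "a minimum of 10 days between termination of the investigational drug and administration of orteronel is required". Section 5.3.2 prohibits chronic systemic corticosteroids on study, but exclusion 19 keeps a patient out only if a prohibited drug cannot safely be stopped or replaced.

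**Analysis.** Section 10.7 summarises observed levels and changes from baseline, with no allowance for therapy stopped around the time of the sample.

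**The concern.** A change from baseline describes orteronel only if the baseline describes the patient without another hormone-active drug. If an earlier drug still holds the hormone down at the draw and its effect then fades, the later sample reflects orteronel plus recovery from that drug. The two effects are mixed, and a fall looks smaller than it was.

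The protocol itself treats such drugs as relevant. Section 3.1 uses LHRH agonists to bring estradiol to the postmenopausal range, and the note on nausea and vomiting in Section 6.1.3.2 links sudden withdrawal of prednisone to acute adrenal insufficiency. Every Cohort 2 patient must have had one to three hormonal therapies, so the estradiol issue lies mainly there. The steroid issue applies to both cohorts.

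Section 1.3 says orteronel had not been studied in this population. The hormone panel is the plan's direct on-treatment measure of whether the drug suppresses sex hormones as Section 1.2 expects. Time of day is a second source of error. Cortisol, ACTH and testosterone vary over the day (general physiology, for which the documents give no figure), so a screening sample and a later sample taken at different hours differ for reasons unrelated to the drug.

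**Working it through.** The plan states no sample size, power or estimate for the hormone endpoint, so there is no figure to reproduce.

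**Step 1: can the draw precede the end of earlier therapy?**
- *Standard endocrine therapy or chemotherapy.* No interval is stated. If exclusion 2 is applied on the day of the draw, concurrent use is ruled out but residual effect is not. If it is applied at enrolment, which Section 4 places after screening, even concurrent use at the draw is possible.
- *Investigational drugs.* The required gap before the first dose is at most 21 days and can be as short as 10. The sampling window is 28 days. Exclusion 5 alone would allow a draw up to 28 - 21 = 7 days, or 28 - 10 = 18 days, before such a drug stops.
- *Steroids.* A patient can be on chronic steroids at the draw and stop before dosing (exclusion 19). Short courses are not on the prohibited list.

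**Step 2: how large could the bias be?** Let s be orteronel's true fractional suppression relative to the untreated level, and a the suppression by earlier therapy still present at the baseline draw. Assume that the earlier effect has gone by the on-treatment sample. Then

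recorded change = (1 - s)/(1 - a) - 1, against a true change of -s.

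The documents give neither s nor a, so both are assumed. Example: s = 0.5, a = 0.75 gives 0.5/0.25 - 1 = +100%. For one patient:

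| True change | a = 0.25 | a = 0.5 | a = 0.75 | a = 0.9 |
|---|---|---|---|---|
| -30% | -6.7% | +40% | +180% | +600% |
| -50% | -33.3% | 0% | +100% | +400% |
| -70% | -60% | -40% | +20% | +200% |
| -90% | -86.7% | -80% | -60% | 0% |

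The sign reverses only when a > s.

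**Step 3: cohort level.** If a share f of patients is affected, the geometric mean change is exp[ln(1 - s) - f ln(1 - a)] - 1. For s = 0.5, a = 0.9, f = 0.25 this is 0.5 × 10^0.25 - 1 = 0.5 × 1.778 - 1 = -11.1%.

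| True change | a | f = 10% | f = 25% | f = 50% |
|---|---|---|---|---|
| -30% | 0.9 | -11.9% | +24.5% | +121.4% |
| -50% | 0.5 | -46.4% | -40.5% | -29.3% |
| -50% | 0.9 | -37.1% | -11.1% | +58.1% |
| -70% | 0.9 | -62.2% | -46.7% | -5.1% |
| -90% | 0.9 | -87.4% | -82.2% | -68.4% |

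The cohort mean changes sign when f exceeds ln(1 - s)/ln(1 - a). At a = 0.9 this is 15% of patients for a true -30%, 30% for -50% and 52% for -70%.

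**Step 4: other hormones.** Section 1.2.2.1 expects ACTH to rise on orteronel. A baseline lowered by steroids would exaggerate that rise. For cortisol and DHEA-S it would hide or reverse a fall.

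**Step 5: what is not touched.** The rules in Sections 10.3 and 10.4 count tumour responses only. No hormone value enters them.

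**The case against.** The strongest reply is that the rules, read together, already keep other therapy away from the draw. Exclusion 2 bars current hormonal therapy, consent precedes every study procedure, and Section 5.3.2 prohibits hormonal therapy and chronic steroids while on study. A site that applies these at the screening draw has no patient on concurrent endocrine therapy. That is a fair reading, and it limits the point: for endocrine therapy, what certainly remains is residual effect. It does not settle the matter for steroids, because exclusion 19 expects some patients to arrive on prohibited drugs and stop them.

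A reader might infer that all 55 Cohort 2 patients have a contaminated baseline. The documents do not support this. The same criterion also requires earlier chemotherapy in the advanced setting, so the last regimen may not have been endocrine, and the plan does not say which hormonal drugs were used or that they lower estradiol. Fifty-five is the cohort size, not the number exposed.

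A reader might also infer that the estradiol changes will carry the wrong sign. That needs assumed values in which the earlier drug suppressed more than orteronel does. Most of the cohort-level values above keep the sign.

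Nor is the information lost altogether. Section 10.7 also reports observed levels, and medical history and concomitant medication are collected, so some later stratification is possible. Without stop dates linked to the sample date, however, it would be incomplete. Finally, the endpoint is descriptive, with no hypothesis or decision rule. All of this bears on severity; none of it supplies a baseline close to dosing.

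**Conclusion.** The point holds as a limited weakness in a secondary, descriptive endpoint. As written, the plan permits a sole baseline up to 28 days before dosing, not tied to the end of endocrine therapy or steroid use and with no time of day, and it analyses unadjusted change from that value. The direction of the bias is predictable for an affected patient: falls are understated, and a rise in ACTH is overstated after steroids. Its size cannot be derived from the documents. In the illustration, a true -50% reads anywhere from -46% (10% of patients affected, half suppressed) to +58% (50% affected, 90% suppressed); with 25% affected at 90% suppression it reads -11%. These values rest on the ratio model, on assumed s, a and f, and on full recovery from the earlier drug by the on-treatment sample. Response rate, disease control rate and both two-stage rules stand as they are. This is a cheap improvement worth making, not a flaw in the trial's main conclusions.

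**What to change.** - In Sections 5.2.1, 7.3 and 7.4.1 and Appendix E footnote j, take the baseline hormone sample on Cycle 1 Day 1 before the first dose. A site that uses estradiol to confirm ovarian suppression keeps its screening estradiol for that purpose.
- Draw the Cycle 1, 2 and 4 Day 1 samples in one consistent morning window, before that morning's dose. Take the End-of-Treatment sample in the same clock window where possible; predose timing has no meaning there. This is a new instruction: footnotes d and e of Appendix E use the term predose only for on-treatment odd-numbered cycles and set no morning window.
- Record the stop date of the last endocrine therapy and of any systemic steroid.
- In Section 10.7, add a summary of change by whether such a drug was taken within 28 days before the baseline sample. When editing that paragraph, reconcile its Cycle 3 Day 1 time point with the Cycle 4 Day 1 draw in the schedule.

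**Cost.** One tube moves to an existing visit, four visits need attention to clock time, two dates are added to the case report form, and one table is added. A Cycle 1 Day 1 draw reduces carry-over but does not eliminate it, since therapy may have stopped shortly before. The added summary would show what remains. The change alters no eligibility or treatment rule.
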